## 1 OBJECTIVES

### 1.1 Primary Objectives

#### 1.1.1 Conspicuity:

- 1.1.1.1 Quantitative MRI: To assess the conspicuity of idealized T1 and T2 imaging at detecting brain metastases at baseline.
- 1.1.1.2 Chemical Exchange Saturation Transfer (CEST) MRI: To assess the conspicuity (CNR) of CEST imaging at detecting brain metastases at baseline.
- 1.1.1.3 Multiple B Value Diffusion Imaging (Adv Diff): To assess the conspicuity (CNR) of Adv Diff at detecting brain metastases at baseline.
- 1.1.1.4 Gradient- and Spin-Echo (GESE) Dynamic Susceptibility Contrast (DSC) perfusion imaging: To assess the conspicuity of GESE DSC and standard Gradient Echo (GE) DSC at detecting brain metastases at baseline.

### 1.2 Secondary Objectives

#### 1.2.1 Conspicuity:

- 1.2.1.1 Quantitative MRI: To assess the conspicuity of T2 imaging at detecting brain metastases on a per-patient basis at follow-up scans and on a per-lesion basis at baseline and at follow-up time points.
- 1.2.1.2 Chemical Exchange Saturation Transfer (CEST) MRI: To assess the conspicuity (CNR) of CEST imaging at detecting brain metastases on a per-patient basis at follow-up scans and on a per-lesion basis at baseline and at follow-up time points.
- 1.2.1.3 Multiple B Value Diffusion Imaging (Adv Diff): To assess the conspicuity (CNR) of Adv Diff at detecting brain metastases on a per-patient basis at follow-up scans and on a per-lesion basis at baseline and at follow-up time points.
- 1.2.1.4 Gradient- and Spin-Echo (GESE) Dynamic Susceptibility Contrast (DSC) perfusion imaging: To assess the conspicuity of GESE DSC and standard Gradient Echo (GE) DSC at detecting brain metastases on a per-patient basis at follow-up scans and on a per-lesion basis at baseline and at follow-up time points.

#### 1.2.2 Treatment Response:

- 1.2.2.1 Quantitative MRI: To assess the trend of idealized quantitative T1 and T2 values of brain metastases compared to normal brain parenchyma following treatment with stereotactic radiosurgery.
- 1.2.2.2 Chemical Exchange Saturation Transfer (CEST) MRI: To assess the ability of CEST imaging to differentiate radiation necrosis from progressive disease in brain metastases following stereotactic radiosurgery.

- 1.2.2.3 Multiple B Value Diffusion Imaging (Adv Diff): To assess whether Adv Diff can differentiate radiation necrosis from progressive disease in brain metastases following stereotactic radiosurgery.
- 1.2.2.4 Gradient- and Spin-Echo DSC perfusion imaging: To assess whether GESE DSC improves differentiation of radiation necrosis from progressive disease in brain metastases following stereotactic radiosurgery compared to standard GE DSC.
- 1.2.2.5 Multiple inversion time (TI) arterial spin labeling (ASL) “Adv ASL” perfusion imaging: To assess the ability of Adv ASL to differentiate radiation necrosis from progressive disease in brain metastases following stereotactic radiosurgery.

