## 2.2 Quantitative MRI

Intensity values on routine MR imaging are not defined in terms of any consistent scale since the signal is dependent on many hardware and patient-specific factors. Hence there is very little gained in measuring the “bright” or “dark” pixel values on an MR image, and the images must be interpreted subjectively. This would be analogous to subjectively describing “hot” or “cold” spots on an infrared heat map image when the absolute temperature scale of the pixels is not known. This study proposes to use multi-parameter mapping to quantitatively measure the signal changes in the tissues to address these challenges. In MR imaging, hydrogen nuclei or “spins” are the sources of the signal. In the strong magnetic field of an MR scanner, these spins emit RF signals in response to transmitted RF pulses. Thus contrast mechanisms in MR imaging are highly dependent on the hydrogen spin density or proton density (PD), as well as the longitudinal and transverse relaxation times (T1 and T2, respectively), which tend to vary between different tissues or fluids. However, measurement of relaxation times requires multiple acquisitions, and as a result measurement or quantitation of these parameters can be excessively long for clinical MR exam.

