### 5.3 Quantitative MRI

- 5.3.1 The largest circular ROI that fits within the brain lesion on axial T1 post contrast imaging will be placed and will define the lesion ROI.
- 5.3.2 The T1 and T2 tissue weighting that maximizes the ROI mean signal intensity will be identified.
- 5.3.3 A mirror ROI will be placed in the contralateral normal appearing white matter and used as the “background” mean signal intensity measurement.
- 5.3.4 An extracranial ROI without visible artifact will be used as the mean “noise” signal intensity measurement.

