## 7.3 Analysis Plan

Patients are expected to have on average four brain lesions each. The primary analysis will be performed on the largest lesion within patients at baseline, and secondary analyses will consider all lesions. The sensitivity of each method at detecting lesions as determined by T1 weighting will be reported with 95% confidence intervals. Analyses will also be performed at the subsequent scans as numbers permit.

For the secondary endpoints that consider treatment response, for each of the imaging methods, at each time point, we will calculate the contrast to noise ratio (CNR) in patients with lesions that respond to treatment and in patients with local failure and will compare these by using a Wilcoxon rank-sum test. If numbers permit, analyses may be repeated using all lesions. Additionally, of the lesions that initially respond, some will subsequently grow in size after the initial response. Of these, some will be considered treatment change and some residual disease. The CNR will be compared between lesions with treatment change and those that are progressive disease using a Wilcoxon rank-sum test.

All statistical tests will be performed with two-sided tests with 5% Type I error rates. No adjustment will be made for the multiplicity of testing. We recognize that the Type I error rate overall will be greater than 5%.

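### No planned analysis follows T1 and T2 values over time, so secondary objective 1.2.2.1 would go unanswered as written

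*Combined protocol and SAP*

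**What the plan says.** The objective in section 1.2.2.1 is "To assess the trend of idealized quantitative T1 and T2 values of brain metastases compared to normal brain parenchyma following treatment with stereotactic radiosurgery". It names a variable (T1 and T2), a comparator (normal brain) and a time course. The other four treatment-response objectives (1.2.2.2 to 1.2.2.5) instead ask whether a method separates radiation necrosis from progression.

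Section 7.3 gives all treatment-response endpoints, for every imaging method, the same two analyses:

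- The first reads "at each time point, we will calculate the contrast to noise ratio (CNR) in patients with lesions that respond to treatment", sets these patients against those with local failure, and "will compare these by using a Wilcoxon rank-sum test".
- The second concerns lesions that grow again after responding: "The CNR will be compared between lesions with treatment change and those that are progressive disease using a Wilcoxon rank-sum test".

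For the quantitative sequence, section 5.3 says "The T1 and T2 tissue weighting that maximizes the ROI mean signal intensity will be identified". The comparator is handled as follows: "A mirror ROI will be placed in the contralateral normal appearing white matter and used as the “background” mean signal intensity measurement". A noise region is also recorded. Section 2.2 gives the reason for using a quantitative method at all: "Intensity values on routine MR imaging are not defined in terms of any consistent scale". It proposes multi-parameter mapping as the remedy.

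**The concern.** The analysis answers a different question from the objective. A test of CNR between outcome groups at one scan shows whether the groups differ then. It does not show how T1 or T2 in treated metastases moves relative to normal brain after radiosurgery. The mismatch begins at measurement, because section 5.3 asks for signal intensities at a chosen weighting rather than T1 and T2 values.

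The repeated quantitative scans are the study's main longitudinal resource. If the plan is followed exactly, the report will contain no estimate and no interval for the trend. Any trend analysis added later would be chosen after the data were seen.

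**Working it through.** **1. The plan's own figures.** No sample-size or precision figure is given for this objective. The only design figure is the 14.5% half-width in section 7.2. It reproduces with the exact (Clopper–Pearson) 95% interval at 25 of 50, which is 35.5% to 64.5%: (64.5 − 35.5)/2 = 14.5 points. It concerns baseline sensitivity and has no bearing here.

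**2. Objective against analysis.**

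| | Objective 1.2.2.1 | 7.3, first test | 7.3, second test |
|---|---|---|---|
| Variable | T1 and T2 values | CNR | CNR |
| Contrast | lesion against normal brain | responders against local failures | treatment change against progressive disease |
| Time | trend after radiosurgery | each scan separately | time point not stated |
| Result | change over time | rank-sum p-value | rank-sum p-value |

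The only other follow-up analysis in section 7.3 repeats the sensitivity estimates at later scans, which serves the conspicuity objectives. Nowhere is there a change from baseline, a slope, a repeated-measures model or a paired lesion-against-normal comparison of T1 or T2.

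**3. Measurement.** Sections 5.5 to 5.8 name the quantity to be read for their methods (AKC and ADC, rCBV, vessel size, CBF and bolus arrival time). Section 5.3 names none. It also does not say whether the signal-maximising weighting is chosen once or afresh at each scan. If afresh, the resulting intensities would not be comparable between scans even within one lesion.

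**4. A shared change is invisible to a between-group test.** Write the value for patient i at time t as y = aᵢ + βt + error, with the same β in both groups. At a given t, the term βt adds one constant to every patient. The ranks do not change, so the rank-sum statistic does not depend on β.

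A simulation illustrates this. All its inputs are assumed: 35 responders and 15 failures, complete data at 8 scans, between-patient SD 1, within-patient SD 0.5 or 1, a common slope of 0.1 or 0.2 SD per scan, and 2,000 runs per setting. The per-scan rank-sum test rejected in 4.0% to 5.9% of runs, about its nominal 5%. A one-sample test of the within-patient slopes rejected in at least 99.6%. This shows the mechanism; it does not measure the loss in this study.

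**5. Time axis.** Section 4.5.2 allows 4 to 16 weeks between scans. If that applies to all seven intervals, the eighth scan falls between 7 × 4 = 28 and 7 × 16 = 112 weeks after the first. Scan number is therefore not a common time scale, and a table by scan number cannot stand in for a trend.

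**6. Data involved.** Fifty patients (section 3.3) × 8 scans (section 4.6.1) = 400 patient-scans. At an average of 4 lesions (section 7.2), 400 × 4 = 1,600 lesion-scans. Both are ceilings. Participation ends on death, patient request or an MR contraindication, and the documents give no attrition rate. Section 7.3 also makes use of all lesions for treatment response conditional on numbers.

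**The case against.** CNR takes contralateral white matter as its background, so it carries part of the comparison with normal tissue. Calculating it at each scan would allow a descriptive table. If responders and failures diverged, the per-scan tests could show a difference at later scans. All of this stands, but none of it gives a T1 or T2 value or an estimate of change.

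The word idealized leaves room for doubt. It may refer to the weighting that section 5.3.2 selects rather than to relaxation times. That ambiguity is fair, and the documents do not settle it. Under either reading no analysis over time is specified.

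A reader might infer that T1 and T2 will not be available at all. The documents do not support that. Section 2.2 describes a mapping method that measures T1, T2 and proton density, and section 4.3 includes quantitative MRI for all patients. What is missing is the readout and the analysis.

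A reader might also recast this as a multiplicity problem and attach a family-wise error rate to a run of tests on T1 and on T2. The documents do not support that either. Section 7.3 does not split quantitative MRI into T1 and T2 tests, scans of the same patients are not independent, and the section openly accepts unadjusted testing. An error rate would in any case say nothing about whether a trend is estimated.

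Finally, a single straight-line slope would be a poor remedy. Sections 7.1 and 7.3 expect some lesions to respond and then regrow, and a line could average that to near zero.

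**Conclusion.** The concern holds and should be fixed. This is more than missing detail: the analyses stated for this objective use a different variable, have no time term and cannot detect a change common to both outcome groups. The objective has no planned estimate, so no percentage loss can be attached to it. The documents give no SD, correlation, attrition rate or target change from which to compute precision for a corrected analysis.

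The effect is confined to one of nine secondary objectives (four on conspicuity, five on treatment response). The conclusion rests on sections 5.3 and 7.3 being the complete specification, since no other section supplies a T1 or T2 readout or a longitudinal method.

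**What to change.** In section 5.3, record mean T1 and mean T2 from the quantitative maps, in the lesion region and the mirror region, at every scan. State what idealized means in the objective.

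In section 7.3, add a longitudinal analysis of the lesion-minus-mirror difference in T1 and in T2, on actual time since radiosurgery rather than scan number. One suitable option is a mixed model with random effects for patient and for lesion within patient, with time in windows or as a spline and not only as a straight line. Report change from baseline with 95% confidence intervals, overall and descriptively by response group. State that loss through death or withdrawal limits the later estimates. Changes from baseline by time window with intervals would also serve. If a trend is not wanted, reword 1.2.2.1 to match the group comparisons.

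The cost is one added region readout per map and one standard model, with a short amendment to sections 5.3 and 7.3. No new scanning is needed, provided that the sequence used yields the maps described in section 2.2.

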## 2 BACKGROUND

### 2.1 Brain Metastasis

Brain metastases have been reported to occur in up to 30% of patients with cancer, and treatment options include supportive care, surgery, and radiotherapy. The incidence of brain metastases is increasing, partly because of increase in the incidence of primary cancers and partly because improvements in treatment options have prolonged survival of patients with cancer, which increases the chance of primary tumors metastasizing. There are very few chemotherapy options open to patients with brain metastases. Stereotactic radiosurgery (SRS) has become an increasingly important treatment option for the initial management of patients with brain metastases. Early and accurate detection of small metastases is associated with improved treatment success. At present, gadolinium-enhanced MRI is considered to be the imaging technique of choice in patients suspected of brain metastases.

Significant limitations to the utilization of gadolinium-enhanced MRI in the screening for brain metastasis is cost and the requirement of an intravenous injection of a contrast agent. Some patients have claustrophobia requiring sedation. Additionally, underlying conditions, such as back pain, may make it hard for the patients to lie still for the duration of the MRI. Achieving standard-of-care MR imaging in these populations can be challenging. There is a vital clinical necessity for a safe and efficient screening imaging technology to offer patients at risk of brain metastases, who have contraindications to gadolinium as well as the ability to tolerate long examination times. Thus, fruitful diagnostic techniques that do not rely on gadolinium injection would be clinically meaningful by improving cost, time and safety of MR imaging.

Current MR imaging protocols for brain metastasis evaluation rely on contrast-enhanced T1-weighted MRI (CE-T1WI), which has proven itself a valuable tool for the visualization of tumor margins. However, changes in lesion size as determined by CE-T1WI images taken alone are not specific to cell death. There has been more success with quantitative MR methods, such as the apparent diffusion coefficient (ADC), which increases with apoptosis and has been correlated with response to therapy. It has also been shown that low pretreatment ADC values are correlated with a favorable response. However, given that ADC is sensitive to many changes in tissue micro-structure, it is often difficult to distinguish between tumor necrosis, edema, or

radiation-induced inflammation, which inhibits its use in monitoring cancer treatment.

Advanced imaging techniques currently in clinical use such as dynamic contrast enhancement perfusion imaging and dynamic susceptibility contrast perfusion imaging have been shown to improve diagnostic accuracy in the assessment of brain metastasis behavior following stereotactic radiosurgery. However, their diagnostic yield is not ideal (sensitivity and specificity less than 90% in clinical trial settings) and their usage is demonstrated in the reactionary scenario following the development of abnormal conventional imaging. These techniques have not been shown to be able to predict future behavior of lesions prior to the development of anatomic imaging abnormalities.

## 2.2 Quantitative MRI

Intensity values on routine MR imaging are not defined in terms of any consistent scale since the signal is dependent on many hardware and patient-specific factors. Hence there is very little gained in measuring the “bright” or “dark” pixel values on an MR image, and the images must be interpreted subjectively. This would be analogous to subjectively describing “hot” or “cold” spots on an infrared heat map image when the absolute temperature scale of the pixels is not known. This study proposes to use multi-parameter mapping to quantitatively measure the signal changes in the tissues to address these challenges. In MR imaging, hydrogen nuclei or “spins” are the sources of the signal. In the strong magnetic field of an MR scanner, these spins emit RF signals in response to transmitted RF pulses. Thus contrast mechanisms in MR imaging are highly dependent on the hydrogen spin density or proton density (PD), as well as the longitudinal and transverse relaxation times (T1 and T2, respectively), which tend to vary between different tissues or fluids. However, measurement of relaxation times requires multiple acquisitions, and as a result measurement or quantitation of these parameters can be excessively long for clinical MR exam.

Recent developments in rapid multi-parameter mapping techniques are possible due to advances in accelerated imaging and reconstruction techniques. These typically incorporate efficient pulse sequence designs and mathematical constraints to assess the desired information in each pixel. SyntheticMR developed the first clinically available method and released by GE Healthcare as "MAGIC" (MAGnetic resonance Image Compilation), which can achieve whole brain quantitation in 5-6 minutes. The SyntheticMR method assumes the process of T1 and T2 relaxation times to be monoexponential, whereas it may be multi-exponential for many tissues. However, a phantom study has revealed good accuracy and reproducibility for T1, T2, and PD measurements by the SyntheticMR method. These measured parameters can also be applied to an MR spin model produce images with almost any contrast weighting by virtually changing repetition time (TR), echo time (TE), and inversion time (TI). Synthetic MRI is particularly useful when many different contrast settings (for example, T1 weighted imaging (WI), T2WI, proton density WI) are required. Synthetic MRI of the brain without the use of a contrast agent has been reported to produce images that although inferior in image quality the diagnostic power of the images was comparable to that of images obtained via conventional MRI sequences. Therefore, if the diagnostic power of images obtained via synthetic MRI after administration of a contrast agent is also proved to be comparable to that of conventional MRI, synthetic MRI could

be a useful means of screening for brain metastases, significantly reducing scan time and providing quantitative data.

## 2.3 Multiple B-Value Diffusion Imaging (Adv Diff)

Molecular diffusion is a stochastic process and, as such, it may be described by probability distributions. The most basic of these is the probability of a molecule moving a given displacement over a given time interval. For simple, homogeneous liquids (e.g., a glass of water), this displacement probability distribution function is Gaussian, and the diffusion is referred to as Gaussian diffusion. In conventional MR imaging, diffusion of water molecules in the tissues has a tiny contribution to the MR signal. In diffusion MRI, powerful magnetic gradients with echo planar sequence are used. Thus, the measurement of the molecular diffusion of water has been possible for decades using MRI, and diffusion-weighted imaging (DWI) with MRI has been possible for greater than thirty years.

A diffusion coefficient called apparent diffusion coefficient (ADC) value can be calculated within each image voxel, and ADC maps can be generated on a pixel-by-pixel basis. Because diffusion coefficients are high in fluids where diffusion is free, a low signal is observed on diffusion imaging at  $b = 1000 \text{ mm}^2/\text{s}$  (high signal on corresponding ADC maps). Normal CSF is an example of this. On the other hand, if the mobility of water molecules is restricted such as in ischemia (cytotoxic edema) high signal is observed on diffusion imaging at  $b = 1000 \text{ mm}^2/\text{s}$  (low signal on corresponding ADC maps).

*Diffusion-weighted imaging* has been proposed as a set of tools to improve diagnostic accuracy and achieve a better understanding of the pathophysiology of brain cancer. A specialized form of DWI is *diffusion tensor imaging* (DTI) that provides information not only about the random displacement, or passive diffusion, of water molecules but also about fiber directionality and integrity. DTI can allow visualization of neuronal projections in the central nervous system and estimation of the neuronal changes in the white matter of healthy subjects and patients with various neurological diseases.

Fractional anisotropy (FA) and mean diffusivity (MD) obtained from diffusion tensor imaging (DTI) has been used to assess the nature of brain metastasis and their response to treatment. However, FA and MD have limitations in accurately evaluating brain metastasis. New technologies, such as *diffusion kurtosis imaging* (DKI), can provide a more informative insight into the biology of tissue including brain metastasis. An advantage of DKI is that it is relatively simple to implement for human imaging on conventional MRI clinical scanners. DKI protocols differ from DTI protocols in requiring at least three b-values (as compared to 2 b-values for DTI) and at least 15 independent diffusion gradient directions (as compared to 6 for DTI). Typical protocols for brain have b-values of 0, 1000, 2000 s/mm^2 with 30 diffusion directions. The **apparent excess kurtosis coefficient** (AKC) is a dimensionless metric that quantifies the degree of deviation from Gaussian diffusion behavior.

Defining the relationship between DKI and brain metastasis prior, during and following treatment can provide more abundant imaging to guide cancer diagnosis and treatment. DKI

has been used to measure the non-Gaussian nature of water diffusion, which can reveal a more complex microstructure in both normal and pathological tissues compared to DTI alone. Previous studies have demonstrated that there was a significant difference in mean kurtosis (MK) value between high- and low-grade astrocytomas. However, to the best of our knowledge, no comparison of different diffusion imaging approaches for assessing brain metastasis has been performed.

